Study Protocol and Statistical Analysis Plan

Document Title: Therapeutic Effects of Kinesiotape in the Management of Gonarthrosis: A Randomized Controlled Approach

NCT Number: NCTXXXXXXXX

Document Date: November 25, 2015

Study Protocol

Study Design

This study is a single-blinded, randomized controlled trial involving 38 individuals diagnosed with gonarthrosis according to ACR classification criteria. Participants are randomly assigned to two groups. Taping group (n=19) received kinesiotape application and a home exercise program, while participants in the control group (n=19) received only a home exercise program

Inclusion Criteria

- Having a diagnosis of primary gonarthrosis according to ACR classification criteria,
- Being between 45 and 65 years of age,
- Having a radiological diagnosis of gonarthrosis between Kellgren-Lawrence stage 1-3,
- Signing the informed consent

Exclusion Criteria

- Presence of a neurological disorder affecting muscle strength or balance,
- History of any surgical operation on the knee, hip, or spine,
- Physiotherapy or injections for the knee within the previous year,
- Presence of systemic conditions such as diabetes mellitus, vertigo, visual problems,
- History of severe trauma within the previous year

Interventions

In the taping group, the Mechanical correction technique and the Ligament/Tendon correction technique were applied using kinesiotape application. The taping procedure was repeated once a week, starting from the first week, for a total of 6 sessions. An individualized home exercise program was planned, considering EULAR and ACR recommendations. Each participant was given a structured home exercise program at least 3 days a week. The program included moderate-intensity aerobic exercises (e.g., walking) and muscle-strengthening exercises targeting the quadriceps and hamstring muscles, along with flexibility and balance exercises.

Outcome Measures

The demographic characteristics (age, gender, education, body mass index) were documented for both groups. The patients were evaluated two times with clinical assessment scales: Visual Analogue Scale (VAS) was used to assess pain, Western Ontario and McMaster Universities Osteoarthritis Index (WOMAC) questionnaire to assess pain, stiffness and functionality, Berg Balance Scale (BBS) to assess balance, Short Form (SF-36) to assess physical function,

physical role, emotional status, social function, general health, mental health, pain, quality of life.

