Statistical Analysis Plan

Sample size was calculated using G-Power 3.1.3 software. The power and “>” levels were set to 0.80 and 0.05, respectively, and the effect size (ES) was set to 0.8. A priori analysis for the required sample size indicated that at least 21 subjects would be needed in each group. Thus, 23 subjects were used in each group to account for dropout cases (Cohen, 1992). The Kolmogorov-Smirnov and Shapiro-Wilk tests were used to determine whether the obtained measurements conformed to normal distribution, and the data were found to be normally distributed. Since the data were normally distributed, parametric tests were used in the comparisons. Whether there was a significant difference between the averages of these parameters measured before and after the treatment between the control and taping groups was analyzed by a t-test in independent groups, and whether there was a significant change between the parameters before and after the treatment in the taping and control groups separately was analyzed by a t-test in dependent groups. The change in parameters from pre-treatment to post-treatment was also analyzed for significant differences between groups using a t-test in independent groups. The data obtained in the research were analyzed using the SPSS (Statistical Package for Social Sciences) for Windows 20.0 program.

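### Each outcome has two unadjusted between-group tests and neither is named as decisive; one baseline-adjusted ANCOVA per outcome should decide

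*Combined protocol and SAP*

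**What the plan says.** The Statistical Analysis Plan section lists three kinds of test for each outcome.

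- **Between groups, at each time point.** The averages "measured before and after the treatment between the control and taping groups was analyzed by a t-test in independent groups". This gives a post-treatment comparison and also a significance test of baseline means.
- **Within each group.** The pre-to-post change "in the taping and control groups separately was analyzed by a t-test in dependent groups".
- **Between groups, on change.** "The change in parameters from pre-treatment to post-treatment was also analyzed for significant differences between groups using a t-test in independent groups".

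No analysis adjusts for baseline. The document names no primary analysis, no primary outcome, no order of tests and no rule for conflicting results. The baseline score is available for each scale, because the Outcome Measures section says: "The patients were evaluated two times with clinical assessment scales".

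Two further statements affect the numbers below. Study Design puts 19 patients in each group ("Taping group (n=19) received kinesiotape application and a home exercise program"), whereas the SAP says: "Thus, 23 subjects were used in each group to account for dropout cases". The SAP also reports a finding from the data: "the data were found to be normally distributed".

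**The concern.** The post-treatment test and the change test address the same treatment effect. In a randomised trial each is valid alone at 5%. With both in the plan and no ranking, a trial that succeeds on only one of them can be reported as positive. The SAP does not say that one success is enough, but it does not exclude it.

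The two tests also differ in power, and which is better depends on a pre/post correlation that the plan does not state. The post-treatment test is stronger when the correlation is below 0.5 and the change test when it is above (with equal SDs). The plan collects the baseline score but has no analysis that weights it according to the data.

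The between-group baseline test adds nothing. Under randomisation any baseline difference is due to chance, so the test is not informative about treatment.

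**Working it through.** **Inputs from the documents.** Effect size 0.8, power 0.80, alpha 0.05, at least 21 per group and 23 with dropout allowance (SAP); 19 per group (Study Design); two assessments (Outcome Measures).

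**Assumptions.** Pre/post correlation ρ from 0 to 0.9; normal data with equal SD before and after treatment; effect 0.8 in post-score SD units; two-sided 0.05. None of these is stated in the documents.

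**1. The plan's own figure.** A two-sample t-test (noncentral t) at effect size 0.8 and 80% power needs 20.03 per group one-sided, rounded up to 21, and 25.52 two-sided, rounded up to 26. So 21 reproduces, but only as a one-sided, unadjusted t-test. At 21 per group the power is 82% one-sided and 72% two-sided.

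**2. Variances of the three analyses**, relative to the post-score variance:

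- post-treatment: 1
- change: 2(1 − ρ)
- ANCOVA: (1 − ρ²) × 35/34 at 19 per group, where 35/34 = 1 + 1/(2×19 − 4) is the price of estimating the slope

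At ρ = 0.5 these are 1, 1 and 0.75 × 35/34 = 0.77. ANCOVA equals the post test at ρ = √(1/35) = 0.17 and the change test at ρ = 2 × 34/35 − 1 = 0.94. Between those values it is the most precise of the three.

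**3. Type I error if either test may be claimed.** The correlation between the post and change differences is (1 − ρ)/√(2(1 − ρ)) = √((1 − ρ)/2), which is 0.71 at ρ = 0 and 0.22 at ρ = 0.9. The tests therefore overlap less as ρ rises, and the error moves towards 1 − 0.95² = 9.75%. Simulation (100,000 trials per setting, 19 per group):

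| ρ | either t-test | ANCOVA |
|---|---|---|
| 0 | 8.3% | 4.9% |
| 0.3 | 8.7% | 4.9% |
| 0.5 | 9.1% | 5.0% |
| 0.7 | 9.3% | 5.0% |
| 0.9 | 9.7% | 5.1% |

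Repeat simulations agree within about 0.3 points. One-sided, the either-test error is 8.3% to 9.3% for ρ from 0.3 to 0.8.

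**4. Power and disagreement at a true effect of 0.8 SD, two-sided.**

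| n per group | ρ | post | change | ANCOVA | t-tests disagree |
|---|---|---|---|---|---|
| 19 | 0.3 | 67% | 53% | 70% | 31% |
| 19 | 0.5 | 67% | 67% | 78% | 30% |
| 19 | 0.7 | 67% | 87% | 91% | 31% |
| 23 | 0.3 | 76% | 61% | 79% | 29% |
| 23 | 0.5 | 76% | 76% | 86% | 26% |
| 23 | 0.7 | 76% | 93% | 96% | 24% |

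Over ρ from 0 to 0.9, disagreement is 30% to 34% at 19 per group and 24% to 34% at 23. The 34% arises at ρ = 0.

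**5. Sensitivity to the assumptions (19 per group).**

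- Post SD 1.3 times the baseline SD: disagreement is 23% to 28% for ρ from 0.3 to 0.7. At ρ = 0.7 the change test (about 92%) and ANCOVA (91%) are level.
- Post SD 0.8 times the baseline SD: disagreement is 38% to 39% over the same range.
- Effect size 0.8 read as change-score SD units, ρ = 0.7: post/change/ANCOVA power is 46/67/73% and disagreement is about 40%.

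**The case against.** The strongest objection is that the inflation argues for naming one test, not for ANCOVA. Naming either existing t-test in advance would also hold 5% within an outcome. That is correct, and the case for ANCOVA then rests on efficiency. The gain over the better t-test is about 3 points at ρ = 0.3, 4 points at ρ = 0.7 and 11 points at ρ = 0.5. What remains is that choosing the better t-test requires knowing ρ, whereas ANCOVA came within about one point of the better t-test, or beat it, in every setting tried.

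Other points also stand in part:

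- The 8% to 10% holds only if either result may be claimed. The SAP's word for the second test could be read as marking it as additional, but the text does not settle this.
- The disagreement figures depend on equal SDs before and after treatment. Relaxing that gives about 23% to 39%, so the missing rule still matters.
- Multiplicity across outcomes is the larger source of error. Counting VAS, three WOMAC domains, the Berg scale and eight SF-36 items gives 13 measures. If these were independent, one 5% test on each would give up to 1 − 0.95¹³ = 49% familywise error. A single ANCOVA per outcome does not address this.
- The SAP is written in the past tense and reports a normality result, so the change may be a post hoc reanalysis and not just an edit of the plan.

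**Conclusion.** The concern holds. The SAP gives each outcome two unadjusted between-group tests of the treatment effect and no decision rule. If either may count, the false-positive rate within an outcome is about 8% to 10% against the intended 5%. With a real effect of 0.8 SD, the conclusion would depend on which test is reported in roughly a quarter to a third of trials (equal SDs; 23% to 39% when that is relaxed). The conclusion is the same at 19 and 23 per group and for one-sided or two-sided testing. The exact sizes rest on the assumed correlation, the equal-SD assumption and the reading of the effect size. Each t-test is valid alone, so this is a change that should be made, not a fatal flaw.

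**What to change.** - Name one ANCOVA per outcome as the decisive between-group test, two-sided at 5%: post-treatment score on group, with that outcome's baseline score as covariate. Report the adjusted difference with a 95% confidence interval, and check linearity and a common slope.
- Label the post-treatment and change t-tests as supportive, or remove them. Treat the within-group paired tests as descriptive, since they do not compare the groups.
- Present baseline values by group without significance tests.
- Name a primary outcome or a multiplicity rule; without one, error across the outcomes stays uncontrolled.
- If data have been seen, declare the ANCOVA post hoc and report the t-tests listed in the SAP beside it.

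**Cost.** The change is SAP wording, or a reanalysis if the data have already been analysed. It needs no new data and runs in the SPSS package already specified. ANCOVA uses one degree of freedom, so below a correlation of about 0.17 it loses about one point of power to the post test (66% against 67% at 0.1). With equal SDs it is also slightly less precise than the change test above about 0.94. Its nominal power is below that of the uncorrected either-test rule (78% against 82% at correlation 0.5, 19 per group), but that rule reaches 82% by spending about 9% alpha.
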